2.2 Secondary Objectives and Secondary Endpoints

Secondary endpoints are divided into five items:

- 1. Course of the disease as described by the following criteria
 - a. Time from remission to first relapse
 - b. Number of relapses during follow-up
 - c. Mean relapse rate per patient and year
 - d. Number of frequent relapsers
 - e. Time from remission to intensification of immunosuppressive treatment with other drugs due to glucocorticoid-induced toxicity
 - f. Rate of patients who require more intense immunosuppressive treatment
- 2. Glucocorticoid-associated toxicity:
 - a. Cumulative prednisone dose as mg/m²
 - b. As there is no validated score for glucocorticoid-induced toxicity, each item is registered separately. At visits 1-8, body mass index, arterial hypertension, and growth failure will be checked for quantitative influence, striae, hypertrichosis, acne, and psychological disturbances by yes or no for qualitative influence. Additionally, at visits 1, 5, and 8, patients will be checked for cataract and glaucoma (by yes or no).

.....

- 3. Mycophenolate mofetil-associated toxicity: At all visits, patients will be checked for known side effects of MMF, especially diarrhea, blood cell count disturbance, and infections.
- 4. Health-related quality of life, which is impaired in children with nephrotic syndrome [21], will be measured with a validated questionnaire (DISABKIDS) at visits 1/5/8.
- 5. Days missing school attendance and days of hospitalization will be documented as a measure for the impact of the disease on everyday life.

It is expected that MMF-based regimen will avoid acute and long-term glucocorticoid-associated toxicity and is therefore superior regarding the benefit/risk ratio. However, this will not be tested confirmatorily since there exists no endpoint/score summarizing the different aspects of side effects.

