Even though being effective, this treatment is associated with pronounced glucocorticoid-associated toxicity due to high-dose prednisone administration over a prolonged period of time. The major side effects, which have been shown consistently in previous studies [3,4,9], comprise obesity, striae, hypertrichosis, cataract, glaucoma, arterial hypertension, psychological disturbances, growth failure, disturbances in carbohydrate and lipid metabolism, osteopenia, and avascular bone necrosis. Not all of these side effects are fully reversible after cessation of steroid therapy. In one study for example, excess weight gain during initial steroid therapy persisted in a significant subset (47%) of patients following cessation of glucocorticoid therapy [10]. Excess weight following cessation of glucocorticoid therapy was associated with hyperlipidemia, which might enhance the cardiovascular risk of these patients in the long-run [11]. Furthermore, a recent GPN study on the initial treatment of the nephrotic syndrome revealed no advantage of an intensified immunosuppressive protocol in terms of occurrence of relapses during a follow-up of 24 months [5]. Other studies have shown that higher exposure to glucocorticoids in the initial therapy leads to more toxicity without a substantial gain of efficacy, which is prevention of future relapses [8,12].

Treatment of relapses

Relapses of idiopathic nephrotic syndrome in childhood are generally treated with glucocorticoids according to a standard regimen 60 mg prednisone/m² BSA per day until the urine is free of protein for three consecutive days followed by alternate day prednisone 40 mg/m² BSA for 4 weeks. Depending on the number of relapses this aggravates the side effects. In case of frequent relapses a glucocorticoid-free therapy (cyclosporine, mycophenolate mofetil) for sustaining remission has to be considered.

Role of mycophenolate mofetil in the treatment of nephrotic syndrome in childhood

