5.4.2 Dosage Schedule

Maximum duration of treatment: 12 weeks after first day of initial treatment of SSNS. Patients will receive the whole medication for the complete intervention period.

Control intervention:

- The Prednisone, which is continued for a total of 6 weeks with the dosage of 60 mg/m² BSA/d (maximum 80 mg), is given once a day (quaque die (QD)), twice a day (bis in die (BID)) or three times daily (ter in die (TID)).
- The Prednisone, which is given for another total of 6 weeks with the dosage of 40 mg/m² BSA (maximum 60 mg) is given on alternate days (every other day) in one dose in the morning

Resorption of prednisone is independent of food intake.

Experimental intervention:

- Mycophenolate mofetil (MMF) is given in a dosage of 1200 mg/m² BSA/d as a suspension (200 mg/mL) until 12 weeks total treatment duration. MMF is given twice a day (bis in die (BID) = every 12 hours (± one hour).
- The suspension of MMF should be mixed in the study center (according to the Fachinformation).
- The persons having care and custody of the child are informed, that MMF should be given 30 minutes before or 60 minutes after food intake.
- For the first two weeks from randomization/visit1 on, prednisone is given with the dosage of 40 mg/m² BSA (maximum 60 mg) on alternate days (every other day) in one dose in the morning

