Second follow-up	Visit 5	9 months after day 1 (= first day of treatment with standard therapy)	± 14 days
Third follow-up	Visit 6	15 months after day 1 (= first day of treatment with standard therapy)	± 14 days
Fourth follow-up	Visit 7	21 months after day 1 (= first day of treatment with standard therapy)	± 14 days
End of study	Visit 8	27 months after day 1 (= first day of treatment with standard therapy)	± 14 days

^{*} In case the patient is randomized into the experimental intervention group at the fifth day after remission has been achieved start of mycophenolate mofetil is possible at the same day or the next day (i.e. day 6 after remission).

Visit 1

Visit 1 is scheduled at the point in time of allocation to the INTENT study and randomization (0-5 days after date of remission). The exact date depends on the time between first day of treatment with standard therapy for first episode of idiopathic nephrotic syndrome in children (= day 1) and the point in time of remission (this may vary between day 5 until day 28).

At visit 1 the history of the patient is documented: Age, gender, postal code (first 4 of 5 digits), known allergies, other chronic diseases, family history concerning kidney disease. Furthermore side effects of the previous standard treatment are retrieved in yes/no manner (Behavioral disturbances since diagnosis: child feels sad, anxious, irritable, as well as euphoric state, aggressive state, nausea, vomiting (defined as a frequency of more than 1 times per day), diarrhea (defined as a frequency of more than 4 loose stools daily), headache, muscle weakness, any new infection (e.g. respiratory tract infection, gastroenteritis, urinary tract infection)). Application of any current medication (other than immunosuppressive agents) is documented.

The physical examination contains investigation of the skin in yes/no manner (acne, cushingoid facies, striae, and hypertrichosis), further pathological organ-specific findings in yes/no/not done manner (lymphadenopathy, pharyngitis, otitis media, heart murmur, arrhythmia, respiratory tract infection, abdominal pain, and muscle weakness) and pubertal status.

Measurement of weight, height (BMI is computed) and blood pressure after 3 minutes rest are done and documented.

A sample of spot urine is analyzed with dip stick (Albustix®) and quantitatively for creatinine, protein, albumin in the laboratory of the study center (urine protein/creatinine ratio is computed).

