The blood test contains: blood cell count (leukocytes, erythrocytes, hemoglobin, and thrombocytes), HbA_{1c} , creatinine, blood urea/blood urea nitrogen (BUN), uric acid, calcium, phosphate, alkaline phosphatase, 25-OH Vitamin D, total protein, albumin, GPT/ALT, IgG, IgE, Cholesterol.

Study specific investigations are:

- 24 h ambulatory blood pressure measurement (24h-ABPM) performed by the study center with documentation of the median of systolic blood pressure (day), of the median of diastolic blood pressure (day), the median of systolic blood pressure (night), the median of diastolic blood pressure (night).
- o **Ophthalmologic investigation** performed by any ophthalmologist will document cataract (yes/no) and glaucoma (yes/no)
- O Health related quality of life (HRQoL) DISABKIDS as standardized questionnaires to assess health related quality of life is used. There exists a parental questionnaire, a questionnaire for children aged ≥8 years and one for children aged 4-7 years of age. Children below 4 years of age will not receive a questionnaire.
- Echocardiography (Echocardio.) is optional for the INTENT study and will be performed by a pediatric cardiologist. The documented parameters are: LVID (left ventricular internal diastolic diameter), LVIS (left ventricular internal systolic diameter), PWT (posterior wall thickness), and IVST (interventricular septic thickness). The LVID index, the LV FS (Left ventricular fractional shortening), LVM (left ventricular mass), LVM index, and LVH (Left ventricular hypertrophy) are computed.

These study specific investigations can be performed in a time frame of -21 days/ +7 days around the visit date.

The persons having care and custody of the child and the patient will be informed about the randomized medication, especially its handling, dosing, intake in relation to food intake and storage (see 5.4.2).

Further, the use of the patients´ diary is explained. Daily dip stick (Albustix®), given medication (if control intervention: dosage of prednisone in mg; if experimental intervention: dosage of MMF in ml and dosage of prednisone in mg), as well as days of missing school, infections, hospitalization, or other events the persons having care and custody of the child feel important to document.

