The blood test contains: blood cell count (leukocytes, erythrocytes, hemoglobin, and thrombocytes), HbA_{1c}, creatinine, blood urea/blood urea nitrogen (BUN), uric acid, calcium, phosphate, alkaline phosphatase, 25-OH Vitamin D, total protein, albumin, GPT/ALT, IgG, IgE, Cholesterol

Study specific investigations are:

- 24 h ambulatory blood pressure measurement (24h-ABPM) performed by the study center with documentation of the median of systolic blood pressure (day), of the median of diastolic blood pressure (day), the median of systolic blood pressure (night), the median of diastolic blood pressure (night).
- Ophthalmologic investigation performed by any ophthalmologist will document (Cataract (yes/no) and Glaucoma (yes/no))
- Health related quality of life (HRQoL) DISABKIDS as standardized questionnaires to assess health related quality of life is used. There exists a parental questionnaire, a questionnaire for children aged ≥8 years and one for children aged 4-7 years of age. Children below 4 years of age will not receive a questionnaire.

Echocardiography (Echocardio.) is optional for the INTENT study and will be performed by a pediatric cardiologist. The documented parameters are: LVID (left ventricular internal diastolic diameter), LVIS (left ventricular internal systolic diameter), PWT (posterior wall thickness), and IVST (interventricular septic thickness). The LVID index, the LV FS (Left ventricular fractional shortening), LVM (left ventricular mass), LVM index, and LVH (Left ventricular hypertrophy) are computed.

These study specific investigations can be performed in a time frame of ±28 days around the visit date.

Visit 6

Visit 6 is scheduled at 15 months (± 14 days) after day 1 (= first day of treatment with standard therapy for first episode of idiopathic nephrotic syndrome in children).

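### Quality of life, 24-hour blood pressure and eye findings have no planned on-treatment value, and their visit 1 window lets the baseline fall after open allocation

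*Protocol*

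**What the plan says.** Protocol section 2.2 lists quality of life as its own secondary item, which "will be measured with a validated questionnaire (DISABKIDS) at visits 1/5/8". It places the cataract and glaucoma check at the same three visits. Section 6.1 lists "24 h ambulatory blood pressure measurement (24h-ABPM) performed by the study center" in the descriptions of visits 1, 5 and 8 and nowhere else. The two on-treatment visits, 2 and 3, name only optional mycophenolic acid monitoring in the MMF arm as a study-specific investigation.

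On the treatment period, section 5.4.2 says: "Maximum duration of treatment: 12 weeks after first day of initial treatment of SSNS". On the aim, section 2.2 says: "It is expected that MMF-based regimen will avoid acute and long-term glucocorticoid-associated toxicity". It adds that this will not be tested confirmatorily.

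For the visit 1 set, section 6.1 says: "These study specific investigations can be performed in a time frame of -21 days/ +7 days around the visit date". Visit 1 is the randomization visit, 0 to 5 days after remission. The trial is open (section 3.1), and the family is told the allocated medication at visit 1 (section 6.1).

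**The concern.** The arms differ in planned treatment only between visit 1 and week 12. An effect that appears under prednisone and fades afterwards can be seen only by measuring during that period. For DISABKIDS, 24h-ABPM and the eye examination, no such measurement is planned. Section 2.2 expects MMF to avoid acute as well as long-term toxicity, and the rationale in sections 1.2 and 1.3 rests on that benefit. Section 1.1 says "Not all of these side effects are fully reversible after cessation of steroid therapy", which leaves room for some effects being transient.

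The second problem is the baseline. If DISABKIDS is answered after the family knows the arm, the answer can reflect hope or disappointment. If 24h-ABPM or the eye examination is done after the randomized drug has started, the value is no longer strictly pre-treatment. Any comparison that uses these values as baseline inherits the distortion, and no later analysis can remove it.

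**Working it through.** The plan states no figure on this point, so the check is calendar arithmetic. Day 1 is the first day of standard therapy, and one month is taken as 365.25/12 = 30.44 days.

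**Randomized period**
- End of treatment (section 5.4.2): 12 × 7 = day 84.
- Visit 1 (section 6.1): remission on day 5 to 28, plus 0 to 5 days, gives day 5 to 33.
- Length of the randomized period: 84 − 33 = 51 days to 84 − 5 = 79 days.

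**On-treatment visits**
- Visit 2: visit 1 + 28 days, so nominally day 33 to 61.
- Visit 3: 11 × 7 = day 77, ± 7 days, so day 70 to 84.
- Both record resting blood pressure, weight and height (BMI), skin signs, behavior questions, HbA1c and cholesterol. Neither has DISABKIDS, 24h-ABPM or an eye examination.

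**Visits 5 and 8**
- Visit 5, nominal: 9 × 30.44 = day 274; 274 − 84 = 190 days after treatment ends.
- Visit 5, earliest possible (visit −14 days, investigation −28 days): 274 − 42 = day 232; 232 − 84 = 148 days after treatment ends.
- Visit 8, nominal: 27 × 30.44 = day 822; 822 − 84 = 738 days after treatment ends.

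**Visit 1 window**
- The +7 side can reach into the first week of randomized treatment: 7/79 = 9% to 7/51 = 14% of the period. A value that falls there by scheduling chance and is meant as baseline is not an on-treatment measurement.
- On the −21 side, anything more than 5 days before visit 1 precedes the remission date, because visit 1 is at most 5 days after remission.

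**When the planned prednisone contrast occurs** (mg/m², dose caps ignored)
- Control: 42 × 60 + 21 × 40 = 3,360.
- MMF arm: (visit 1 day − 1) × 60 + 7 × 40. Visit 1 on day 5 gives 4 × 60 + 280 = 520; on day 12, 11 × 60 + 280 = 940; on day 33, 32 × 60 + 280 = 2,200.
- Contrast: 2,840, 2,420 and 1,160 respectively, all given by week 12.

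**Relapse treatment by visit 5 and visit 8**
- Assumption: the stated 51% relapse at 24 months with a constant hazard from the end of treatment. Hazard = −ln(0.49)/24 = 0.0297 per month.
- Relapsed by visit 5: 1 − exp(−0.0297 × 6.24) = 17%, and more if relapses come early. By visit 8: about 51%.

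**The case against.** The strongest reply is that acute toxicity is measured on treatment. Visits 2 and 3 cover resting blood pressure, BMI, acne, cushingoid facies, striae, hypertrichosis, behavior, HbA1c and cholesterol. Adverse events are collected from the first dose to visit 4 (section 7.2). The hypertension endpoint of section 2.2 is checked at every visit, and 24h-ABPM is not named there. Quality of life is a separate item, introduced because the disease impairs it, and all secondary outcomes are descriptive (section 8.4). All of this stands. A reader might infer that the acute-toxicity aim as a whole cannot be answered. The documents do not support that: the gap is confined to three measures, under a non-confirmatory expectation.

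A reader might also infer that eye, blood-pressure and quality-of-life effects will have gone by visit 5, so that the comparison there is bound to show nothing. Section 1.1 does not say so. It calls some effects not fully reversible, and its one figure is excess weight persisting in 47%. A lasting cataract would still be visible at visits 5 and 8.

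Relapse prednisone is a consequence of the assigned strategy, so its presence at visit 5 is no error in itself. On the constant-hazard assumption, visit 5 is the off-treatment point least affected by it (17% against 51% at visit 8). Moving the set from visit 5 to visit 3 would give that up. It would also measure controls in their alternate-day phase, after the daily phase has ended.

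On the baseline, a value taken up to 21 days early precedes allocation and adds noise to both arms rather than bias. The protocol fixes no change-from-baseline analysis for these measures, and some allowance is practical because any ophthalmologist may examine the child. None of this answers the post-allocation side of the window, least of all for a questionnaire that can be completed during the visit.

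**Conclusion.** The point holds for three measures only. DISABKIDS, 24h-ABPM and the eye examination have no planned value between 7 days after visit 1 and about day 232, whereas randomized treatment ends on day 84. They can show residual or long-term differences between arms; a difference confined to the treatment period would be missed. How much is missed depends on how transient the effects are, and the protocol gives no figure for that.

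The baseline weakness is separate and does not depend on reversibility. In an open trial, up to 7 days of the visit 1 window lie after disclosure and possibly after the start of randomized drug. The risk is greatest for the self- or parent-reported DISABKIDS. It is smaller for 24h-ABPM, and the protocol gives no reason to expect new eye findings within a week.

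The primary endpoint, the sample size and the confirmatory test are unaffected.

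**What to change.** 1. Require the visit 1 DISABKIDS to be completed before the allocation is disclosed. The cost is the order of steps within one visit.
2. Use 24h-ABPM and eye results as baseline only if obtained before the first dose after randomization. The cost is a few missing baselines where the examination cannot be arranged in time.
3. Keep all visit 5 assessments and also give DISABKIDS at the existing visit 3, whose window closes at the end of treatment. The cost is one more questionnaire per family and an eCRF page. Children already past visit 3 when the amendment takes effect would lack the value.
4. For 24h-ABPM and eye findings, leave the schedule as it is and state in section 2.2 that they address residual and long-term effects, with on-treatment toxicity described by the items recorded at visits 2 and 3. This changes wording only.

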3.2 Study Duration and Schedule

The duration of the study for each subject is expected to be 27 months (including 24 months follow-up after intervention)

Study duration:

Total study duration: [78 months] Duration of clinical phase: [63 months] Beginning of the preparation phase: [03/2014] FSI (first subject in): [01/2015] LSI (last subject in): [01/2018] LSO (last subject out): [04/2020] DBL (database lock): [07/2020] Statistical analyses completed: [08/2020] Study report completed: [04/2021]

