4.2 Inclusion Criteria

Subjects meeting all of the following criteria will be considered for admission to the study:

- First episode of steroid-sensitive nephrotic syndrome (SSNS)
- In remission induced by daily glucocorticoids within 28 days
- Male and female children aged ≥ 1 year and ≤ 10 years at beginning of study (typical age range of patients with SSNS)
- Ability of the persons having care and custody of the child to understand character and individual consequences of clinical study
- Written informed consent of the persons having care and custody of the child (must be available before enrolment in the study)

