5.5 Randomization

5.5.1 Randomization method

All patients who seem suitable for study participation and take part in the screening, will be registered in a screening log and receive a screening number. Together with the center id this will be the unique identification number throughout the study. At the end of the screening phase the suitability of the patient is assessed finally.

When the patient is included in the study (all inclusion criteria fit and none of the exclusion criteria apply), he will be given a consecutive randomization number according to the randomization tool. Patients withdrawn from the study retain their number.

To achieve comparable intervention groups, patients will be allocated in a concealed fashion by means of randomization using a centralized web-based tool (www.randomizer.at). Randomization will be performed stratified by age groups (grouped: <7 years of age), because age is known to influence the occurrence of relapses. If the randomizer is not available in urgent cases the Institute of Medical Biometry and Informatics can be contacted ([name]) and a biometrician or data manager will perform the randomization.

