The persons having care and custody of the child are instructed to interpret the results of the Albustix[®] and are instructed to react as described. In doubt the persons having care and custody of the child are encouraged to contact the study center early.

Albustix™	Interpretation	Consequence
Negative	No relapse	Nothing to do
Trace		
30 mg/dL = +	doubtful value	 Daily weight investigation for edema (yes/no) The urine protein/creatinine ratio (Up/c) or a specimen of a urine collection has to be analyzed, if 1+ appears for 3 days or 1+ is combined with ≥2+ within 3 days.
100 mg/dL = ++		
300 mg/dL = +++	Relapse, if detected on 3 consecutive days	Contact study center
≥2000 mg/dL		
= ++++		

Visit 2

Visit 2 is scheduled at 4 weeks after visit 1 (± 5 days).

At visit 2, the history since visit 1 is documented, especially if one or more relapses occurred since visit 1.. In case of a relapse, date of first day of relapse (definition fulfilled) is documented. For each relapse, it is documented, according to which criteria the relapse was diagnosed: Albustix $\geq 2+$ (>30mg/dL) for 3 consecutive days, Spot urine: Up/c ratio ≥ 2 g/g, or collecting urine: Up excretion of ≥ 40 mg/m² BSA/h. If the relapse was treated, the medication is recorded. Further, date of remission is documented (see definitions). In order to document possible trigger factor infections during relapse (e.g. respiratory tract infection, gastroenteritis) and vaccinations within two weeks prior to the relapse are recorded, too. All information from the diary (days missing school attendance, days of hospitalization since last visit are recorded. According to diary and patients inquiry adherence to study medication is assessed (Reduction of study medication > 50%?, Pause of study medication > 3 days?).

Side effects of the treatment are retrieved in yes/no manner (Behavioral disturbances since visit 1: child feels sad, anxious, irritable, as well as euphoric state, aggressive state, nausea, vomiting (defined as a frequency of more than 1 times per day), diarrhea (defined as a frequency of more than 4 loose stools daily), headache, muscle weakness, any new infection).

Application of any current medication (other than immunosuppressive agents) is documented.

The event of renal biopsy since last visit is recorded with histology.

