All secondary outcomes will be evaluated descriptively, using appropriate statistical methods based on the underlying distribution of the data. Descriptive p-values are reported together with 95% confidence intervals for the corresponding effects. Descriptive statistics for continuous parameters and scores include number of non-missing observations, mean, standard deviation, median, minimum and maximum, performed for treatment groups as well as subgroups and overall. The description of categorical variables (ordinal or nominal) includes the number and percentage of patients belonging to the relevant categories in the study population as well as to each treatment group.

Rates of adverse and serious adverse events will be calculated with 95% confidence intervals for treatment group comparisons.

Statistical methods are used to assess the quality of the data, homogeneity of treatment groups, endpoints and safety of the two intervention groups. Details of the statistical analysis will be fixed at the latest in the Statistical Analysis Plan (SAP) to be prepared within the first year after start of patient recruitment. All persons taking part in the preparation of the SAP and possible

later changes to it will only have access to blinded data to avoid introduction of bias. All analyses will employ SAS Version 9.2 or higher.

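### Secondary item 5 records only missed school days in a trial that enrols from age 1, with no attendance status and no kindergarten or day-care absence described (minor)

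*Protocol*

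**What the plan says.** Section 2.2, item 5, defines the measure: "Days missing school attendance and days of hospitalization will be documented as a measure for the impact of the disease on everyday life". It is the last of five groups of secondary endpoints and does not appear among the key secondary endpoints in the synopsis.

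The data come from the family diary. Section 6.1 (visit 1) lists what families enter: daily dipstick, medication given, "as well as days of missing school, infections, hospitalization, or other events" that they think worth noting. From visit 2 on, site staff transfer the counts: "days missing school attendance, days of hospitalization since last visit are recorded". The same instruction recurs at every visit up to visit 8, with no age condition.

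The population is "Male and female children aged ≥ 1 year and ≤ 10 years at beginning of study" (section 4.2). On follow-up, section 3.2 says: "The duration of the study for each subject is expected to be 27 months".

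The visit 1 history covers age, gender, postal code, allergies, other chronic diseases and family kidney history. School, kindergarten or day-care attendance is not listed there or at any later visit. For quality of life, by contrast, section 6.1 does set an age rule: "Children below 4 years of age will not receive a questionnaire".

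On analysis, section 8.4 says "All secondary outcomes will be evaluated descriptively", with methods suited to the distribution of the data and details left to the SAP.

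**The concern.** A child can miss school only while enrolled in one. Over an entry range of 1 to 10 years and 27 months of follow-up, many children will be below school age for part or all of their time in the study. For that time the item yields a zero or a blank whatever the disease does to the family's daily life. A three-year-old kept out of kindergarten for two weeks contributes nothing, unless a parent reads school to include kindergarten, and then the count depends on how each family understood the word.

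An SAP can choose a denominator or restrict by age, since age is recorded. It cannot recover what was not collected: whether and from when a child attended, and absence from kindergarten or day care.

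The gap also overlaps with quality of life. By the protocol's wording, children get no questionnaire while under 4, so of items 4 and 5 little beyond hospital days describes the youngest patients. Section 2.2 expects the experimental regimen to have the better benefit/risk balance but does not test this confirmatorily, so descriptive measures like this one are part of what readers will have.

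**Working it through.** **No figure to reproduce.** The protocol gives no number for this item: no expected days missed, no age distribution, no school starting age. The sample size in section 8.1 rests on the primary endpoint alone and is not involved.

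**Inputs from the protocol.** Entry age 1 to 10 years (section 4.2); follow-up T = 27/12 = 2.25 years (section 3.2).

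**Inputs assumed.** School entry at age c = 6 or 7. Entry age either uniform on 1 to <11 years, or triangular on 1 to 11 with its peak at 3. Absence occurs at a constant rate during school time.

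**Formulas.** With F the distribution function of entry age:
- not at school age at visit 1: F(c)
- never at school age during the study: F(c − T)
- share of child-time at school age: s = (1/T) ∫ from 0 to T of [1 − F(c − t)] dt

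Uniform: 1 − F(x) = (11 − x)/10, so s = (11 − c + T/2)/10.
- c = 6: (5 + 1.125)/10 = 0.61
- c = 7: (4 + 1.125)/10 = 0.51

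Triangular: 1 − F(x) = (11 − x)²/80 for x ≥ 3, so s = [(11 − c + T)³ − (11 − c)³]/(3 × 80 × T).
- c = 6: (7.25³ − 5³)/540 = (381.08 − 125)/540 = 0.47
- c = 7: (6.25³ − 4³)/540 = (244.14 − 64)/540 = 0.33

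| Entry ages (assumed) | School entry | Below school age at visit 1 | Never reach it in the study | Share of time s |
|---|---|---|---|---|
| Uniform, 1 to <11 | 6 | 50% | 27.5% | 0.61 |
| Uniform, 1 to <11 | 7 | 60% | 37.5% | 0.51 |
| Triangular, peak 3 | 6 | 69% | 34% | 0.47 |
| Triangular, peak 3 | 7 | 80% | 51% | 0.33 |

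**Wider assumptions.** Uniform ages 1 to 10 give s = 0.68, 0.57 and 0.46 for school entry at 5, 6 and 7. Log-normal entry ages with medians of about 3.5, 4 and 5 years and school entry at 6 give 0.26, 0.34 and 0.50. The lowest case, median 3.5 and entry at 7, gives 0.15. If families count kindergarten from age 3 as school, s is about 0.9.

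**Effect on an all-child mean.** If time outside school scores zero and d is the difference per 27 months at school, the difference per randomised child is s × d. For an illustrative d of 6 days this is 6 × 0.33 = 2.0 to 6 × 0.61 = 3.7 days. Both arm means shrink by the same factor, so their ratio is unchanged: (s × m₁)/(s × m₀) = m₁/m₀.

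**The case against.** The strongest reply is that the protocol never says missed days will be averaged over all children. Section 2.2 says only that they are documented, and section 8.4 leaves the method to the distribution of the data and the SAP. Denominator, age restriction and offset belong in an SAP, and age is on file for restricting to older children. This stands. It rules out a reading that a reader might otherwise take from the arithmetic, namely that the plan dilutes the difference between arms to one third to two thirds. That factor belongs to an analysis the protocol does not specify and to an assumed age mix and school starting age.

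A second tempting inference is bias between arms. The documents do not support it: "Randomization will be performed stratified by age groups (grouped: <7 years of age", a cut close to the assumed school starting age, so time out of school should be similar in both arms. The cost is in precision and interpretation.

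Third, the diary and eCRF forms are not shown, the diary summary allows free-text events, and school is not defined as excluding kindergarten. This stands in part. Free text is not systematic capture, though, and an undefined term read differently by different families is itself a reason to define it.

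Finally, hospital days, the other half of item 5, apply at every age, and the item is secondary and descriptive. Both are correct and limit the severity.

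None of this answers the data-capture gap. An age cut only approximates enrolment, most poorly for children who start school during follow-up, and it recovers no pre-school absence.

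**Conclusion.** The point holds as a minor defect in data capture. As described, the school-day measure cannot show the burden on daily life for pre-school children, and a zero or blank cannot be fully told apart from full attendance. Under the tabulated assumptions, 27.5% to 51% of children never reach school age in the study. The shrinkage of an absolute difference, to about 0.33 to 0.61 in those scenarios and about 0.15 to 0.9 more widely, is conditional on averaging over all children and on assumed ages, so it should be quoted only with those conditions. The primary endpoint, the sample size, hospital days and the comparability of the arms are untouched.

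**What to change.** Change item 5, the diary line and the visit item to *days absent from school, kindergarten or day care*. At each visit, record whether the child attends one of these and since when. In the SAP, report absent days per attended time among attending children, for example as a rate with attendance time as offset. Keep hospital days as the measure for all children and report it separately.

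The cost is one reworded diary line, one eCRF field and a sentence in the SAP. Children who attend nothing do not contribute to this item, and the report should give their number by arm. For children already in follow-up when the change is made, attendance can be asked from the next visit; kindergarten or day-care absence before then stays uncollected, and the report should say so.
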